Appendix 3. Analysis Windows for Reporting

The below applies to certain windowed summaries and analyses (eg, descriptive statistics by visit, change from baseline by visit, etc.). Windows will be based on the patient's date of first dose of study medication; the first day of dosing is Day 1.

Adverse events, however, do not follow windows.

If there is more than one observation in a specific window, then the one closest to the target day will be selected for analysis. If there are two observations that are equidistant to the target day, then the first of these two observations will be selected for analysis. If there are two or more observations on the same selected day within the same analysis window, then the mean of these observations will be used.

| Week | Target Day | Analysis Window |
|----------|------------|----------------------|
| Week 5 | 29 | Day 2 to Day 57 |
| Week 13 | 85 | Day 58 to Day 113 |
| Week 21 | 141 | Day 114 to Day 169 |
| Week 29 | 197 | Day 170 to Day 225 |
| Week 37 | 253 | Day 226 to Day 281 |
| Week 45 | 309 | Day 282 to Day 337 |
| Week 53 | 365 | Day 338 to Day 393 |
| Week 61 | 421 | Day 394 to Day 449 |
| Week 69 | 477 | Day 450 to Day 505 |
| Week 77 | 533 | Day 506 to Day 561 |
| Week 85 | 589 | Day 562 to Day 617 |
| Week 93 | 645 | Day 618 to Day 673 |
| Week 101 | 701 | Day 674 to Day 729 |
| Week 109 | 757 | Day 730 to Day 785 |
| Week 117 | 813 | Day 786 to Day 841 |
| Week 125 | 869 | Day 842 to Day 897 |
| Week 133 | 925 | Day 898 to Day 953 |
| Week 141 | 981 | Day 954 to Day 1009 |
| Week 149 | 1037 | Day 1010 to Day 1065 |
| Week 157 | 1093 | ≥ Day 1066 |

Additional weeks if needed are derived by adding 8 weeks onto Week, and adding 56 days onto Target Day. Lower and upper bounds are also adjusted by adding 56 days.

| Endpoint | Classificati on | Population | Descriptive analysis | Inferential analysis |
|-------------------|--------------------|------------|--------------------------------|-----------------------------|
| Proportion with | Primary | AT* | Number and % | Point estimate and |
| responding bone | 5 | | | CI using Clopper- |
| lesions at NaF-3 | | | | Pearson method |
| | | | | |
| Heterogeneity of | Secondary | AT* | Summary stats | |
| response at NaF-3 | | | and histograms | |
| | | | | |
| CCI | | | | |
| | | | | |
| | | | | |
| | | | | |
| | | | | |
| | | | | |
| | | | | |
| | | | | |
| | | | | |
| | | | | |
| | | | | |
| | | | | |
| | | | | |
| | | | | |
| | | | | |
| | | | | |
| | | | | |
| | | | | |
| | | | | |
| | | | | |
| | | | | |
| | | | | |
| | | | | |
| | | | | |
| | | | | |
| | | | | |
| | | | | |
| | | | | |
| | | | | |
| | | | | |

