5.4 Safety Follow-Up

All patients will have safety follow-up after permanent discontinuation of study drug (enzalutamide). Safety follow-up should occur approximately 30 days after the last dose of study drug or before initiation of cytotoxic chemotherapy, a lutamide (bicalutamide, nilutamide, or flutamide), or a new investigational therapy, whichever occurs first. In the event that one of these treatments is initiated before safety follow-up occurs (eg, a physician not associated with protocol MDV3100-18 initiates the treatment, and study site personnel are not aware of the treatment until afterward), safety follow-up should be scheduled as soon as possible.

If treatment is discontinued due to an adverse event or serious adverse event, the event(s) must be followed up as described in [Section 8.3.6](#). For patients who refuse further clinic study visits, telephone contact should be attempted and documented to review for adverse events through approximately 30 days after the last dose of study drug or before initiation of cytotoxic chemotherapy, a lutamide (bicalutamide, nilutamide, or flutamide), or a new investigational therapy, whichever occurs first. There is no long-term follow-up phase.

Safety follow-up procedures are listed in [Table 8](#).

Table 8: Safety Follow-Up Procedures

Activity / Assessment	Comment
General Activities	
Complete physical examination	Measure vital signs (temperature, blood pressure, heart rate) and weight. ECOG performance status (Table 13). Assess systems per standard of care at the study site.
Adverse events review	Record any new or ongoing adverse events.
Concomitant medications review	Record any new medications or changes in ongoing medications.
Study drug accountability	Collect all remaining study drug and record study drug returned.
Local Laboratory Evaluations	
Serum chemistry, hematology	Refer to analytes listed in Table 12.
PSA	

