10.6 Determination of Sample Size

The total number of patients to be included in this study is approximately 20 and is based on practical clinical considerations.

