- [6] At investigator discretion (eg, significant bone pain or a skeletal-related event for ^{99m}Tc-MDP bone scintigraphy; or suspicion of soft tissue disease progression for CT or MRI) or (for ^{99m}Tc-MDP bone scintigraphy only) to coincide with NaF-3 unless bone disease progression was confirmed earlier. Progression at week 13 or earlier will require a confirmatory ^{99m}Tc-MDP bone scintigraphy at least 6 weeks later showing at least 2 additional new lesions related to prostate cancer (compared with the previous scan). After week 13, no confirmation of progression will be required if at least 2 new lesions related to prostate cancer are observed. If no bone disease progression was seen by ^{99m}Tc-MDP bone scintigraphy before NaF-3, then ^{99m}Tc-MDP bone scintigraphy will be required at the time of NaF-3. Send copies of bone scintigraphy images to the central imaging vendor for archiving.
- [7] Includes vital signs (temperature, blood pressure, heart rate), ECOG performance status, weight. Height at screening only.
- [8] May skip if performed within prior 3 days.
- [9] Symptom-directed and includes vital signs, ECOG performance status, and weight.
- [10] Repeats every 16 weeks ±7 days after week 21.
- [11] Collect serious adverse event information from the time of signed informed consent and nonserious adverse event information from the time of first dose of study drug through 30 days after the last dose or initiation of cytotoxic chemotherapy, a lutamide (bicalutamide, nilutamide, or flutamide), or a new investigational therapy, whichever occurs first. Phone patients for follow-up if they do not come to the clinic.
- [12] Complete, sign, and fax or email the form with requested items to the medical monitor or designee at least 2 business days before the anticipated day 1 visit, if possible. Patient may proceed to day 1 visit when medical monitor or designee approves by signed form or email correspondence.
- [13] Patients with PSA values increased from baseline may discontinue study drug and have safety follow-up unless the investigator considers continuation of study drug to be beneficial.
- [14] Refer to laboratory and imaging instruction manuals for sample processing and imaging acquisition requirements. Interpretation of ¹⁸F-NaF PET/CT imaging performed at the central imaging vendor.
- [15] Collect predose.
- [16] At time of NaF-3.

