5.2.2. Nominal Timepoints

Visit windows will apply per Appendix 3. Analysis Windows for Reporting.

Note that NaF-1 and NaF-2 are scheduled for baseline and week 13, respectively. NaF-3, however, is more fluid and can occur depending on different disease progressions or 2-years of therapy, per Section 3.1. If NaF-3 occurs before the scheduled NaF-2, then that scan will be NaF-3, and the pre-planned NaF-2 will not exist.

For endpoints only collected once post-baseline at NaF-3 (eg, circulating tumor cells), the NaF-3 slotted value will be the measurement closest to the NaF-3 scan.

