6.6.4. Laboratory Data

Laboratory data in this study consist of hematology values and chemistry tests. Only data collected from the central laboratory during the treatment-emergent period will be summarized. Laboratory data collected outside the treatment-emergent period will only be listed in the data listings.

Laboratory results will be converted to International System of Units (SI) units which will be used for applying toxicity grades and for all summaries.

Quantitative data will be summarized using simple descriptive statistics (mean, standard deviation, median, quartiles, minimum, and maximum) of actual values and change from baseline for each nominal visit over time (ie, unscheduled assessments will be excluded). The total number of patients for change from baseline will include all patients in the treatment arm who have both a baseline and a value at the nominal visit.

As described in Section 3.4, baseline will defined as the last assessment performed on or prior to date of the first dose of study treatment. If there are multiple assessments that meet the baseline definition on the same day without the ability to determine which was truly last, then the worst grade will be assigned as the baseline grade.

Results collected as strict inequalities (eg, >10, <10) will be converted to numeric values by subtracting a factor of <0.001>. Expressions of the form" \geq " or " \leq " will be converted to the end point. These numeric values will be evaluated for clinically significant abnormalities, but will not be included in calculations of summary statistics.

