6.6.7. ECOG

[figure not shown]
Descriptive summaries at baseline and at the safety follow-up will be provided. These include:

• Number and percentage of patients for each of the six categories.

The ECOG performance status scores will be listed.

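### SAP Appendix 3 has no safety follow-up row, so off-drug lab, vital-sign and weight results would be labelled as the next treatment week

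*SAP*

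**What the plan says.** SAP 5.2.2 states "Visit windows will apply per Appendix 3. Analysis Windows for Reporting". Appendix 3 describes its scope as "The below applies to certain windowed summaries and analyses (eg, descriptive statistics by visit, change from baseline by visit, etc", and gives the rule as "Windows will be based on the patient's date of first dose of study medication; the first day of dosing is Day 1". The table runs from Week 5 to Week 157 in contiguous windows, the last one open-ended. Adverse events are the only stated exemption. There is no row for safety follow-up and no exclusion of results taken after the last dose.

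SAP 6.6.4 summarizes laboratory values and change from baseline "for each nominal visit over time (ie, unscheduled assessments will be excluded". SAP 6.6.5 summarizes blood pressure and weight at scheduled time points. For ECOG, by contrast, SAP 6.6.7 says "Descriptive summaries at baseline and at the safety follow-up will be provided".

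Protocol 5.4 says "Safety follow-up should occur approximately 30 days after the last dose of study drug", or earlier if one of the listed therapies is about to start. Its Table 8 includes hematology, chemistry, vital signs, weight and PSA. Under SAP 3.5 the on-treatment period ends 30 days after the last dose, or when a listed therapy starts if that is sooner. Safety data outside it are listed only.

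For hematology, chemistry and the brief physical examination (which carries vital signs and weight), footnote 10 of Protocol Appendix 2 says "Repeats every 16 weeks ±7 days after week 21". PSA stays on an 8-week schedule.

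**The concern.** Safety follow-up is a scheduled visit, so removing unscheduled results does not remove it. If it falls within 30 days of the last dose it also passes the on-treatment filter. The only remaining rule that decides where it appears is the study-day window, and that rule does not ask whether the patient was still on drug.

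Two effects would follow in the by-visit tables. In weeks 37, 53, 69 and so on, values from patients who had stopped would be mixed with values from patients under treatment. In weeks 29, 45, 61 and so on, where no lab or vital sign is scheduled, the row would describe stopped patients alone. Rows would then alternate between two different groups, and a reader could take the difference for a change over time on enzalutamide.

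**Working it through.** **Inputs.** Window bounds: SAP Appendix 3. Follow-up timing: Protocol 5.4. Sixteen-week schedule: Protocol 5.2.5 (Table 5) and Appendix 2, footnote 10. Thirty-day limit: SAP 3.5. Half-life of 5.8 days: Protocol 8.2.2.

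**1. Reproduce the table.** Target day = 7 × (week − 1) + 1, and window = target − 27 to target + 28. For week 29: 7 × 28 + 1 = 197, window 170 to 225. This reproduces all 20 rows, apart from the open upper end of Week 157.

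**2. Weeks with no scheduled lab or vital sign.** Scheduled weeks are 5, 13, 21, 37, 53, 69, 85, 101, 117, 133 and 149. The rows left over are 29, 45, 61, 77, 93, 109, 125, 141 and 157. A scheduled visit up to 7 days off target stays in its own window (week 37: days 246 to 260, inside 226 to 281), so it cannot fill those rows.

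**3. Where a follow-up lands.** Let the last visit target be T and the last dose be day T + j, with j = 0 to 55. The next window runs from T + 29 to T + 84. A follow-up f days after the last dose falls in it when 29 ≤ j + f ≤ 84.
- f = 30: j ≤ 54, so 55/56 = 98.2%. The one exception goes a window further.
- f = 14: j ≥ 15, so 41/56 = 73.2%.

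Counting every last-dose day from 85 (week 13) to 731 (2 × 365.25 = 730.5), 647 days in all:

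| Follow-up, days after last dose | In next week's window | In a week with no scheduled lab or vital sign |
|---|---|---|
| 14 | 467/647 = 72.2% | 296/647 = 45.7% |
| 21 | 551/647 = 85.2% | 303/647 = 46.8% |
| 28 | 635/647 = 98.1% | 310/647 = 47.9% |
| 29 | 647/647 = 100% | 311/647 = 48.1% |
| 30 | 636/647 = 98.3% | 312/647 = 48.2% |

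Over whole cycles from week 21 (days 141 to 924) the last column is exactly 50%. The shorter range gives a little less, because follow-up at 30 days after a last dose on days 85 to 139 lands in week 21, which has scheduled labs.

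Examples at 30 days: last dose day 141, follow-up day 171, shown as Week 29; last dose day 253, follow-up day 283, shown as Week 45.

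**4. Effect of the 30-day limit.** If follow-up is spread evenly over 30 ± 3, ± 7 or ± 14 days, the share at or before day 30 is 4/7 = 57%, 8/15 = 53% or 15/29 = 52%. The share of all follow-ups that are both summarized and placed in a week without scheduled assessments is then roughly 0.48 × 0.52 = 25% to 0.48 × 0.57 = 27%. Visits brought forward because a listed therapy is about to start would raise the retained share.

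**5. Are these values off drug?** 30/5.8 = 5.2 half-lives, and 0.5^5.17 = 2.8% of parent drug remains, assuming first-order elimination.

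**The case against.** The SAP nowhere says that safety follow-up is slotted into week windows. Appendix 3 covers certain summaries. Labs are summarized by nominal visit, and safety follow-up has its own column in the protocol schedule. ECOG keeps it as a separate timepoint. A programmer could reasonably do the same for labs and vital signs. This stands as far as it goes: the slotting is what the written rule produces, not something the SAP announces. But Section 5.2.2 applies the windows to nominal timepoints, only adverse events are exempt, and labs and vital signs get no counterpart to the ECOG sentence.

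Several stronger readings are tempting and are not supported:
- **That the intermediate weeks are empty of on-treatment data altogether.** PSA is scheduled every 8 weeks, so those rows do hold on-treatment PSA, and the 8-week grid is right for it. Whether PSA is summarized by visit cannot be seen in the public SAP.
- **That nearly all follow-ups are mislabelled.** The 98% and 48% assume follow-up exactly at day 30 and evenly spread last-dose days. Follow-ups after day 30 are only listed. Exits clustered at week 13 would mostly land in week 21. Patients still on drug at data cutoff would have no follow-up visit yet.
- **That counting these values as on-treatment is itself an error.** Both documents define the period to run through 30 days after the last dose. Only the week label is in question.
- **That the trial's safety conclusions would be distorted.** Sample size is "approximately 20 and is based on practical clinical considerations", so there are at most about 20 such visits. The tables are descriptive and report N, so a row of one or two patients would be visible.

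The laboratory part also depends on another conflict. SAP 6.6.4 summarizes only central-laboratory results, while Protocol 8.4 and 12 send safety labs to local laboratories. Taken literally, no lab value would reach the table. Vital signs and weight are affected either way.

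**Conclusion.** The point holds in limited form, and it is minor. For hematology, chemistry, vital signs and weight, the literal rule would usually label a safety follow-up taken within 30 days of the last dose as the next treatment week. It would also leave the rows for weeks 29, 45, 61 and so on made up essentially of patients who had stopped. The share in the next week's window runs from about 72% at 14 days to between 98% and 100% at 28 to 30 days. The share in weeks with no scheduled assessment is about 46% to 48% of follow-ups at those times, or about a quarter of all follow-ups once the 30-day limit is applied under the even-spread assumption. All of this rests on evenly spread last-dose days, visits on target, and reading silence in Appendix 3 as no exemption. The primary and secondary endpoints, adverse events, worst-grade shift tables, liver-test elevations and grade 3/4 listings do not depend on the week labels.

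**What to change.** In SAP Appendix 3:
- Add a separate safety follow-up timepoint, and state that safety follow-up results never enter a week window, in line with Section 6.6.7 for ECOG.
- For labs, vital signs and weight after week 21, show only the 16-week rows (37, 53, 69 and so on). Keep the 8-week rows for PSA.
- State that follow-up values within the on-treatment period still count in the worst-post-baseline tables.

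In SAP 6.6.4, reconcile the central-laboratory restriction with the protocol's use of local laboratories, so that the lab tables have data.

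The cost is SAP wording and a programming change. No new data are needed.

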Appendix 4. Summary of Efficacy Analyses

| Endpoint | Classificati on | Population | Descriptive analysis | Inferential analysis |
|----------|--------------------|------------|--------------------------------|--------------------------------|
| CCI | | | | |
| | | | | |
| | | | | |
| | | | | |
| | | | | |
| | | | | |
| | | | | |
| | | | | |
| | | | | |
| | | | | |
| | | | | |
| | | | | |
| | | | | |
| | | | | |
| | | | | |
| | | | | |
| | | | | |
| | | | | |
| | | | | |
| | | | | |
| | | | | |

| Endpoint | Classificati on | Population | Descriptive analysis | Inferential analysis |
|----------|--------------------|------------|--------------------------------|--------------------------------|
| CCI | | | | |
| | | | | |
| | | | | |
| | | | | |
| | | | | |
| | | | | |
| | | | | |
| | | | | |
| | | | | |
| | | | | |
| | | | | |
| | | | | |
| | | | | |
| | | | | |
| | | | | |
| | | | | |
| | | | | |
| | | | | |
| | | | | |
| | | | | |

| Endpoint | Classificati on | Population | Descriptive analysis | Inferential analysis |
|----------|--------------------|------------|--------------------------------|-----------------------------|
| CCI | UII | | unurysis | unurysis |
| | | | | |
| | | | | |
| | | | | |
| | | | | |
| | | | | |
| | | | | |
| | | | | |
| | | | | |
| | | | | |
| | | | | |
| | | | | |
| | | | | |
| | | | | |
| | | | | |
| | | | | |
| | | | | |
| | | | | |
| | | | | |
| | | | | |
| | | | | |
| | | | | |
| | | | | |

| Endpoint | Classificati on | Population | Descriptive analysis | Inferential analysis |
|----------|--------------------|------------|--------------------------------|--------------------------------|
| CCI | | | | |
| | | | | |
| | | | | |
| | | | | |
| | | | | |
| | | | | |
| | | | | |
| | | | | |
| | | | | |
| | | | | |
| | | | | |
| | | | | |
| | | | | |
| | | | | |
| | | | | |
| | | | | |
| | | | | |
| | | | | |
| | | | | |

| Endpoint | Classificati on | Population | Descriptive analysis | Inferential analysis |
|----------|--------------------|------------|--------------------------------|--------------------------------|
| CCI | | | | |
| | | | | |
| | | | | |
| | | | | |
| | | | | |
| | | | | |
| | | | | |
| | | | | |
| | | | | |
| | | | | |
| | | | | |
| | | | | |
| | | | | |
| | | | | |
| | | | | |
| | | | | |
| | | | | |
| | | | | |
| | | | | |
| | | | | |

[figure not shown]
Protocol MDV3100-18 (C3431012) (Enzalutamide) Statistical Analysis Plan

| Endpoint | Classificati on | Population | Descriptive analysis | Inferential analysis |
|----------|--------------------|------------|-----------------------------|--------------------------------|
| CCI | | | | |
| | | | | |
| | | | | |
| | | | | |
| | | | | |
| | | | | |
| | | | | |
| | | | | |
| | | | | |

Chg: change; bsl: baseline; Obs: observed, LSMean: least-squares mean

* And non-missing scans at NaF-1 and NaF-3.

CCI

10. ABBREVIATIONS

| AE | Adverse event |
|--------|--|
| ANCOVA | Analysis of covariance |
| ALT | Alanine aminotransferase |
| AST | Aspartate aminotransferase |
| AT | As treated |
| BLQ | Below the level of quantification |
| CI | Confidence interval |
| CSR | Clinical study report |
| CTC | Circulating tumor cells |
| CTCAE | Common terminology criteria for adverse events |
| EpCAM | Epithelial cell adhesion molecule |
| GM | Geometric mean |
| HR | Hazard ratio |
| KM | Kaplan-Meier |
| LOA | Limit of agreement |
| LSMean | Least-squares mean |
| MedDRA | Medical dictionary for regulatory activities |
| NCI | National Cancer Institute |
| OM | Observed margins |
| PSA | Prostate specific antigen |
| PT | Preferred term |
| RECIST | Response evaluation criteria in solid tumors |
| SAP | Statistical analysis plan |
| SOC | System organ class |
| StD | Standard deviation |
| SUV | Standardized uptake value |
| TEAE | Treatment emergent adverse event |
| ULN | Upper limit of normal |
